#### **12.4 If this study has undergone scientific or scholarly review, please indicate which entity performed the review:**

- Cancer Center Protocol Review Committee (PRC) (Full approval is required prior to final CHR approval for cancer-related protocols.)
- CTSI Clinical Research Center (CRC) advisory committee
- Departmental scientific review
- Other:

Specify **Other:**

Alzheimer's Association peer review  
Kaiser Permanente Northern California IRB

## **13.0 Background**

### 13.1 Background:

More than 5 million Americans are currently living with Alzheimer's disease and related dementia (ADRD), and prevalence is expected to rise to 14 million by the year 2050. Current dementia medications are associated with relatively small effect sizes and are often discontinued due to side effects. However, there is growing evidence that non-pharmacologic interventions can help reduce symptoms in those who are affected as well as caregivers. The available evidence suggests that multi-domain programs—those that combine physical, mental and social stimulation with caregiver education—are more likely to impact multiple outcomes, yet few multi-domain programs have been rigorously tested and disseminated to the community.

We recently developed a novel, multi-domain, non-pharmacologic program called Paired PLIÉ (pronounced 'plee-ay' and stands for Preventing Loss of Independence through Exercise). The original PLIÉ program was developed and tested at an adult day center with affected individuals and trained exercise instructors, where there was evidence of improvement with PLIÉ versus standard chair-based exercises. Effect sizes were moderate to large in both affected individuals and caregivers (see below). Over the past year, we have adapted PLIÉ to be performed with affected individuals and their primary care partners (Paired PLIÉ), including creation of an illustrated booklet and videos to support home-based practice. **The primary objective of the proposed study is to test the efficacy of the Paired PLIÉ program on participant and caregiver outcomes over 9 months.**

**Sub-Study:** According to feedback from study participants, most dyads have difficulties performing regular exercises at home. The 30-minute video we had supplied did not seem to be effective in supporting home practice. We are now planning a qualitative sub-study to determine whether improving support material in form of brochures or shorter video clips can enhance the motivation and feasibility of home exercises.

### 13.2 Preliminary studies:

Our group has recently pioneered a novel, multi-domain program called Preventing Loss of Independence through Exercise (PLIÉ, pronounced 'plee-ay'). PLIÉ integrates physical activity (training of procedural memory for basic daily activities such as transitioning safely between sitting and standing), cognitive stimulation (mindful body awareness), social engagement (group movement and sharing of in-the-moment experiences), music, and caregiver education (monthly home-visit). We studied PLIÉ in individuals with mild to moderate dementia who were attending an adult day program in San Francisco, CA, and found evidence that those who participated in PLIÉ for 45 minutes, 2-3 days per week for 4 months (total: 26-39 hours) experienced improvements in a wide range of outcomes compared to a Usual Care (UC) control group that participated in standard chair-based exercises. Standardized, between-group effect sizes were moderate to large on validated measures of quality of life (0.83), cognitive function (0.76) and caregiver burden (0.49).

Although PLIÉ was originally designed and tested in an adult day care setting, most people in the community do not have access to a day care center, are concerned about the stigma associated with day care or are unable to afford it. **There is a huge need for innovative, rigorously-tested programs that can be performed together by affected individuals and their care partners, either in group settings or at home.** The Paired PLIÉ Program was specifically designed to address this critical need in the community. Over the past year, we have systematically created the Paired PLIÉ program by adapting the original PLIÉ protocol to be performed by dyads of affected individuals and care partners.

## 14.0 Sample Size and Eligibility

### 14.1 Number of subjects that will be enrolled at UCSF and affiliated institutions:

60 dyads

### 14.2 Total number of subjects that will be enrolled at all sites (Help Text updated 9/13):

60 dyads

### 14.3 Estimated number of people that you will need to consent and screen here (but not necessarily enroll) to get the needed subjects:

100 dyads

### 14.4 Explain how and why the number of subjects was chosen (Help Text updated 9/13):

Sample size estimates and power calculations are based on a repeated measures design with 1 pre and 3 post measures using between-group effect size estimates from our pilot study, correlation between measures of 0.75 (based on our pilot data) and alpha=0.05. Sample size estimates at 80% power ranged from n=8/group to n=22/group depending on the effect size. Conversely, power estimates using a sample size of 30/group ranged from 91% to 100%. Power will be >80% for all outcomes even with 20% attrition. We also estimate that 60% of those screened will be eligible and agree to participate based on our previous studies. There we anticipate screening a total of 100 dyads in order to reach our target sample size of 60 dyads.

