## 11.0 Study Design

### 11.1 \* Study design (Help Text updated 9/13):

We propose to perform a randomized, controlled trial (RCT) with a delayed start design to examine the effects of the Paired PLIÉ program in individuals with cognitive impairment and their care partners over 9 months. Study participants will be 60 pairs of individuals with mild-to-moderate cognitive impairment and their primary care partners. Study pairs will be enrolled in blocks of 10 and will be randomly assigned to Group 1 (immediate start, n=5) or Group 2 (3-month delayed start, n=5). Pairs randomized to Group 1 will participate together in the Paired PLIÉ program 2 days/week for 12 weeks (24 classes total) while pairs randomized to Group 2 will continue with their usual activities. After 3 months, Group 1 will transition into a maintenance phase, and Group 2 will participate in the Paired PLIÉ program 2 days/week for 12 weeks. Outcome data will be collected in all study participants at baseline and 3, and 6 months. We have partnered with local community-based organizations that have agreed to serve as study sites and to assist with recruitment efforts.

We will conduct a sub-study with semi-structured interviews in a sub-sample of our participants. The goal is to assess motivations and barriers for home practice of the exercises taught in the intervention classes and to develop improved support materials (brochures, video clips on DVD and/or YouTube) according to feedback from participants.

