## 12.0 Scientific Considerations

### 12.1 Hypothesis (Help Text updated 9/13):

This study has a hypothesis:

- Yes
- No

If yes, state the hypothesis or hypotheses:

Hypothesis 1: The immediate start group will experience significantly greater improvements in participant outcomes including cognitive function (Alzheimer's Disease Assessment Scale-cognitive subscale, ADAS-cog), independence (Disability Assessment for Dementia, DAD) and quality of life (Quality of Life in Alzheimer's Disease, QOL-AD) compared to the delayed start control group.

Hypothesis 2: The immediate start group will experience significantly greater reductions in caregiver burden (Caregiver Burden Inventory, CBI) and improvements in positive feelings about caregiving (Positive Aspects of Caregiving, PAC) compared to the delayed start control group.

There are no hypotheses for the sub-study.

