#### **12.2 \* List the specific aims:**

Aim 1. To determine whether Paired PLIÉ improves participant outcomes over 9 months.

Aim 2. To determine whether Paired PLIE improves caregiver outcomes over 9 months.

Sub-Study: To develop improved support material for home practice.

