#### **12.3 Statistical analysis:**

All primary analyses will be performed using intent-to-treat principles. Baseline characteristics will be compared using descriptive statistics (e.g., frequency tables and percentages for categorical variables; means, medians, standard deviations, ranges for continuous variables), and p-values will be calculated using appropriate statistical tests (e.g., chi-square, t-test, Mann-Whitney). Our primary analytic approach will be mixed effects linear regression which will enable efficient estimation of intervention effects and inclusion of all subjects in intent-to-treat analyses. Analyses will focus on differences in outcomes between the groups over time. Fixed effects terms will be included for group (immediate vs. delayed start), time (0, 3, 6 or 9 months), and the interaction between group and time, with time modeled as a dummy variable. Subjects and cohorts will be modeled as random effects. Models also will adjust for any baseline differences between groups that may occur by chance. Covariates will be included to adjust for any co-interventions that may occur (e.g., medication changes). Sensitivity analyses will be performed to determine the effects of compliance on intervention effects. Graphs and diagnostic tests will be used to assess for outliers and influence points. Line plots will be used to visually examine change over time by group.

Sub-Study: We will conduct qualitative analyses of the transcribed audio recordings from 10 interviews..

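### The power in 14.4 treats all three post-baseline visits as treated versus untreated, but the control group takes the programme after month 3 and 12.3 names no contrast; for the smallest pilot effect, month-3 power is 77% (change score) or 82% (baseline-adjusted), against a stated 91%

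*Combined protocol and SAP*

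**What the plan says.** Section 14.4 describes calculations "based on a repeated measures design with 1 pre and 3 post measures", using between-group effects from the pilot, a correlation of 0.75 between measures and alpha 0.05. It reports 8 to 22 per group for 80% power and 91% to 100% power at 30 per group, and adds: "Power will be >80% for all outcomes even with 20% attrition". Section 13.2 gives three pilot effects: 0.83 (quality of life), 0.76 (cognitive function) and 0.49 (caregiver burden).

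In the design (11.1), Group 2 continues usual activities for three months only: "After 3 months, Group 1 will transition into a maintenance phase, and Group 2 will participate in the" same 12-week programme.

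The model in 12.3 has group, time at 0, 3, 6 or 9 months, and "the interaction between group and time, with time modeled as a dummy variable". On what will be tested it says: "Analyses will focus on differences in outcomes between the groups over time". The hypotheses in 12.1 compare immediate with delayed start and give no time point. The aims in 12.2 run to nine months, for example "To determine whether Paired PLIE improves caregiver outcomes over 9 months".

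**The concern.** Averaging three post-baseline visits raises power if the group difference holds at each of them. In a delayed-start design there is no reason to expect that. Once Group 2 has taken the programme, the difference at months 6 and 9 depends on how well Group 2 responds and how well Group 1 keeps its gain, and 14.4 is silent on both.

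Section 12.3 does not settle the matter. A model with dummy time and interaction can estimate the month-3 difference, an average over visits, a joint interaction test or a crossover contrast, and their power differs widely. Section 14.4 is the only justification for 30 per group. If no contrast is fixed, the choice can also be made after the results are seen.

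**Working it through.** **Inputs.** Correlation ρ = 0.75, alpha 0.05 and 30 per group (14.4); 24 per group after 20% attrition; effects d = 0.49, 0.76 and 0.83 SD (13.2). Assumed: two-sided test, normal approximation, equal correlation between all visits, no clustering by cohort.

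**Formulas.** The variance of a between-group contrast is 2f/n.
- Mean of r post visits minus baseline: f = (1 − ρ)(1 + 1/r).
- Month 3 adjusted for the baseline score: f = 1 − ρ².
- n per group for 80% power = 2f(1.960 + 0.842)²/d². Power comes from z = d/√(2f/n).

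**Step 1: reproduce 14.4.** With r = 3, f = 0.25 × 4/3 = 0.3333.
- n for 80% power: 21.8 (d = 0.49), 9.1 (0.76), 7.6 (0.83), so 8 to 22.
- Power at 30 per group: 90.8% (0.49) to 100% (0.83).
- Power at 24 per group, d = 0.49: 84%.

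All the stated figures match. Alternatives do not match the full set: three-visit baseline-adjusted (18 and 7 per group; 95%), post-only mean (55 and 19; 55%), two post visits (25 and 9; 87%), one-sided (18 and 6; 95%). Section 14.4 does not tie 91% to an outcome. The link to caregiver burden is inferred, because 0.49 gives both 22 per group and 91%.

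**Step 2: month 3 only.** Change score: f = 0.25 × 2 = 0.50. Baseline-adjusted: f = 1 − 0.5625 = 0.4375.

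| Effect | Method | n for 80% | Power, 30/group | Power, 24/group |
|---|---|---|---|---|
| 0.49 | change | 33 | 76.5% | 67.0% |
| 0.49 | adjusted | 29 | 81.8% | 72.8% |
| 0.76 | change | 14 | 98.6% | 96.1% |
| 0.83 | change | 12 | 99.5% | 98.2% |

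The 24-per-group column puts all losses before month 3. If losses were spread evenly over nine months (an assumption), 30 × (1 − 0.20/3) = 28 would remain at month 3, and power for 0.49 would be 74% or 79%.

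**Step 3: 14.4's own formula after crossover.** Let g be Group 2's response as a share of Group 1's, with gains kept. The group differences at months 3, 6 and 9 are d, (1 − g)d and (1 − g)d, so the three-visit contrast is d[1 + 2(1 − g)]/3. The documents give no value for g. For d = 0.49 at 30 per group:
- g = 0: 0.490 SD, 91%.
- g = 0.5: 0.327 SD, 59%.
- g = 1: 0.163 SD, 19.5%. In this case cognition has 40% and QOL-AD 46%.

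**Step 4: joint group-by-time test, 3 df.** With differences (d, 0, 0), the noncentrality is (n/2) × d² × 0.75/0.25 = 1.5nd². This is 10.8 at 30 per group and 8.64 at 24, giving 80% and 69%.

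**Step 5: a contrast that uses the crossover.** Month 3 minus the mean of months 0, 6 and 9 has f = 0.25 × (1 + 1/3) = 0.3333 and difference d[1 − 2(1 − g)/3]. For d = 0.49:
- g = 1: 91% at 30 per group, 84% at 24.
- g = 0.75: 0.408 SD; 78% and 69%.
- Equal fading in both groups (75%, then 50% retained): 0.49 × (1 + 0.5/3) = 0.572 SD; 97% and 93%.
- With gains kept, 80% power needs g of at least 0.78 at 30 per group and 0.93 at 24.

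**Step 6: outcomes without a pilot effect.** DAD and PAC are hypothesis outcomes (12.1), but the documents give no effect size for them. By month-3 change score the detectable difference at 80% power is 2.802 × √(2 × 0.50/n): 0.51 SD at 30 per group and 0.57 SD at 24.

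**The case against.** Nothing in 14.4 is miscalculated, and the level it states is attainable in this design: the Step 5 contrast can be estimated from the 12.3 model and gives 91% and 84% under equal, lasting effects. That is correct, and it is why the fix below offers that route. But 12.3 does not specify that contrast, and its power depends on Group 2's response.

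The comparison of 82% with 91% also mixes methods. The stated 91% is a change-score figure, so the like-for-like falls are 91% to 77% by change score and 95% to 82% baseline-adjusted. Month-3 power therefore stays above 80% at 30 per group with baseline adjustment. Section 12.3 does say "Models also will adjust for any baseline differences between groups that may occur by chance", but it does not clearly commit to adjusting for the baseline score of each outcome. In either case 20% attrition takes the figure below 80%.

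The shortfall at month 3 is narrow: of the three outcomes with a pilot effect, only caregiver burden falls below 80%. The values of g and the fading pattern are assumptions, so they show sensitivity and predict nothing. A t-distribution lowers the month-3 figures slightly, to 75% and 81%. Effect sizes for DAD and PAC may exist in the pilot publications; these documents do not give them.

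**Conclusion.** The concern holds. The stated power describes a three-visit average with a difference of pilot size throughout. That constant effect is inferred from the exact match, since 14.4 does not state it. The design does not support it by default, and 12.3 pre-specifies no test to which the figure would apply.

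On the month-3 comparison, a true effect of 0.49 is missed about one time in four to one in five, against one in eleven as stated. The claim of more than 80% power for every outcome after 20% attrition fails for caregiver burden at month 3 under either method, and is not shown for DAD and PAC. The direction is secure. The exact percentages rest on ρ = 0.75, equal correlation between visits and no cohort clustering.

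**What to change.** Choose one of two routes.

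**(A) Month 3 as primary.** In 12.3, name the group-by-month-3 difference as the primary contrast and restate 14.4 on it. By change score: 12 to 33 per group for 80% power; at 30 per group, 77% (caregiver burden), 99% (cognition) and over 99% (QOL-AD); at 24 per group, 67%, 96% and 98%. If 12.3 commits to adjusting for the baseline score: 10 to 29 per group, with 82% and 73% for caregiver burden.

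**(B) Keep 91% and 84%.** Pre-specify in 12.3 a contrast or model that uses Group 2's later treatment, such as month 3 minus the mean of months 0, 6 and 9, or a time-varying exposure term. State the post-crossover assumption in 14.4 with a range: 91% and 84% for equal lasting effects, higher if effects fade equally, 78% and 69% if Group 2's response is 25% smaller.

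Under either route, limit the power claim to outcomes with a stated pilot effect and give detectable differences for DAD and PAC. Also reconcile the visit list in 11.1 (baseline, 3 and 6 months) with 12.3 and 16.1, which include month 9. With two post visits, 14.4's own method gives 87%.

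**Cost.** One sentence in 12.3 and a reworded 14.4, with no added participants, visits or procedures. Route (A) means accepting a lower figure for caregiver burden. Holding 80% there after 20% attrition would take 33/0.8, or 42 per group, by change score, or 29/0.8, or 37, baseline-adjusted.

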### 14.5 \* Eligible age range(s):

- 0-6 years
- 7-12 years
- 13-17 years
- 18+ years

### 14.6 Inclusion criteria:

*Affected individuals:* cognitive impairment (mild to moderate severity based on Clinical Dementia Rating of 0.5, 1 or 2); ambulatory and able to take 2 steps without cane or walker; living in the community in a private home or apartment; English language fluency.  
*Caregiver/care partner:* motivated to participate with affected individual; able to answer study questions related to the affected individual's functional status, mood, behaviors, falls, urinary incontinence, and quality of life and their own feelings regarding caregiving; English language fluency.

#### 14.7 Exclusion criteria:

*Affected Individuals:* behavioral or physical issues that would be disruptive or dangerous to themselves or others (e.g., active psychosis, drug abuse, severe behavioral issues); planning to move to a facility before the end of the study period; terminal illness (life expectancy < 1 year); non-stable dementia medication dose; current participation in another research study; unwilling to be video-recorded for quality control purposes.

*Caregiver/care partner:* planning to place affected individual in an institutional setting during the study period; terminal illness (life expectancy < 1 year); behavioral or physical issues that are disruptive or dangerous; unwilling to be video-recorded for quality control purposes.

#### 14.8 There are inclusion or exclusion criteria based on gender, race or ethnicity:

Yes  No

If **yes**, please explain the nature and rationale for the restrictions:

### 15.0 Other Approvals and Registrations

#### 15.1 \* Do any study activities take place on patient care units:

Yes  No

If **Yes**, attach a letter of support for the study from the involved patient care manager(s).

#### 15.2 \* Does your protocol involve any radiation exposure to patients/subjects? The UCSF Radiation Safety Committee requires review of your protocol if it includes administration of radiation as part of standard of care OR research exposures:

Yes  No

#### 15.3 \* This study may generate genetic data that may be broadly shared (e.g. submitted to NIH for Genome-Wide Association Studies (GWAS) in dbGaP, TCGA, etc):

Yes  No

#### 15.4 \* This study involves administration of vaccines produced using recombinant DNA technologies to human subjects:

Yes  No

#### 15.5 \* This study involves human gene transfer (NOTE: Requires NIH Recombinant DNA Advisory Committee (RAC) review prior to CHR approval):

Yes  No

**15.6 This study involves other regulated materials and requires approval and/or authorization from the following regulatory committees:**

Institutional Biological Safety Committee (IBC)

Specify BUA #:

Institutional Animal Care and Use Committee (IACUC)

Specify IACUC #:

Radiation Safety Committee

Specify RUA #:

Radioactive Drug Research Committee (RDRC)

Specify RDRC #:

Controlled Substances

## 16.0 Procedures

**16.1 \* Procedures/Methods (Help Text updated 9/13) For clinical research list all study procedures, test and treatments required for this study, including when and how often they will be performed. If there are no clinical procedures, describe the Methods:**

**1. Recruitment/Screening.** We have partnered with local community-based organizations (see other study sites section) that have agreed to serve as study sites, provide space for the classes and assist with recruitment efforts. In addition, we will circulate flyers throughout the community in neighborhoods surrounding the study sites and will post announcements in newsletters and online (e.g., Facebook). Caregivers will be screened for eligibility by telephone. If the caregiver is not the legally authorized representative (LAR) for the affected individual, the LAR will be contacted separately regarding the affected individual's eligibility. We will mail a letter to the LAR or legal guardian and invite her/him to contact us by mail or phone to discuss the study and the consent process. If we do not get a response within 2 weeks we will call the LAR or legal guardian by phone assuming that she/he has received our letter. The screening and eligibility questions for the affected individual will then be completed with the LAR or legal guardian. The Clinical Dementia Rating (CDR) will be performed to assess level of severity of cognitive impairment. We will continue with enrollment only if the LAR permits the affected individual's study participation.

**2. Informed consent.** Verbal consent to be screened will be obtained over the telephone prior to collecting information on demographics and medical and psychiatric history. Written consent will be obtained with the affected individuals and caregivers/LARs together if possible, as described in more detail below. The consent forms will be reviewed and capacity to consent will be assessed in affected individuals based on responses to questions to determine level of understanding of study procedures, risks, benefits and rights. Participants who do not demonstrate capacity to consent will be asked to assent to study procedures and LARs will be asked to consent on their behalf. Separate consent will be obtained for public release of videos and future contact. After the consent process has been completed, the Montreal Cognitive Assessment (MoCA) will be administered to affected individuals to directly assess level of cognitive impairment. Consent procedures will take place at the study site, home or other location based on individual preferences. If consent is obtained at a location without a photocopier, we will send photocopies of signed consent and HIPAA documents to study participants by mail within 1 week of the consent visit. If there are errors or corrections on the consent or HIPAA forms, we will initial and date and send the updated forms to participants by mail.

Capacity to consent will be assessed by research assistants who will be extensively trained by the PI using a standardized procedure. We first provide the consent form to the affected individual and LAR/caregiver together if possible and allow them to review it. We then describe the key

points of the form, pointing to the areas on the form where the information is described in more detail. We then ask a series of yes/no questions to assess understanding of the information in the form. If the participant cannot answer the questions, we review the material again and reassess their understanding. If they lack capacity to consent, we ask them if they would like to participate in the study to obtain their assent. We say that we are going to ask their LAR to sign the form on their behalf to obtain written consent. Most of our research assistants have a background in psychology and are highly sensitive to working with vulnerable individuals. We train new research staff by having them role play the consent process until senior personnel determine that they are adequately prepared. They then observe senior personnel performing the consent process on at least one study participant. Subsequently they are observed performing the consent process until senior personnel determine that they are competent. We also have weekly team meetings to discuss any difficulties that arise during consent or any other study procedure.

**3. Randomization/Masking.** The randomization sequence will be created in advance using a random number generator. Randomization will be performed in blocks that will vary in size (e.g., 2, 4 or 6) to ensure adequate balancing of the groups. The randomization sequence will be stored separately and securely and will be accessible only to the intervention team. Research staff involved with enrollment and assessment will be blinded and will be unaware of the randomization sequence.

**4. Intervention:** The intervention is an adapted version of the PLIE protocol, which we developed in consultation with experts worldwide who have experience performing different types of exercises in individuals with mild-to-moderate dementia, including physical therapy, occupational therapy, yoga, Tai Chi, Feldenkrais, Rosen and dance movement therapy. Specifically, we have identified exercises from each of these traditions that engage the muscles most needed to maintain independence--including lower body strength (to help with getting out of bed/chair), balance (to minimize risk of falls), upper body strength (to help with lifting), fine motor exercises (to help with activities such as eating and brushing teeth), and pelvic floor exercises (to help with continence)--and we have combined them into a unique integrative exercise program. These exercises are designed to be purposeful (i.e., to achieve a goal) and to build procedural ('muscle') memory. In addition, breathing and guided meditation exercises are included to promote in-the-moment body awareness, relaxation and well-being. Personally meaningful musical selections are also included to promote social connection and shared movement. Exercise instructors may perform an initial goals assessment to learn about preferences, motivators and concerns of caregivers and affected individuals. The intervention will be delivered for 1 hour, 2 days/week for 12 weeks (24 classes total) in a class setting with up to 5 dyads and at least 1 instructor per 5 individuals. In addition, a monthly home visit may be offered during the intervention period to facilitate practice at home (1 hour, 3 visits total). Caregivers will be provided with written materials about the program and will be asked to write weekly reflections of their thoughts and feelings about the content.

**5. Assessments.** We will perform a variety of standard measures in all participants and caregivers at baseline, 3, 6 and 9 months. Data will be collected separately in affected individuals and caregivers to maximize the validity of data collected (e.g., to ensure that caregivers do not 'help' affected individuals with answers to questions and feel comfortable providing information about issues such as difficult behaviors or levels of stress). Affected individuals assessments will take place at the study site. Caregiver assessments will primarily consist of questionnaires that can be self-administered. Therefore, these assessments may occur in person, by phone, or may be returned by email or standard mail, depending on caregiver preference. The first line of communication will be via telephone or in person to minimize the risk of loss of privacy. At the caregiver participant's request, further communication may be conducted via mail, email, fax or text. Caregivers will be informed that these modes of communication may increase their risk of loss of privacy. Mail, email, fax and text communications will include a confidentiality statement. The minimum amount of identifying information will be included in all communications. Study forms will include unique study ID numbers only.

